6.2.2. Kansas City Cardiomyopathy Questionnaire (KCCQ)

The KCCQ [[Green 2000](#)] is a 23-item self-administered questionnaire developed to independently measure the patient's perception of health status, which includes heart failure symptoms, impact on physical and social function, and how their heart failure impacts their quality of life within a 2-week recall period.

The KCCQ quantifies 6 domains (symptoms, physical function, quality of life, social limitation, self-efficacy, and symptom stability) and 2 summary scores (clinical and overall summary [OS]). The KCCQ-OS will be assessed for the first secondary endpoint.

The KCCQ questionnaire will be completed at the timepoints specified in the Schedule of Assessments ([Table 1](#) and [Table 2](#)).

6.2.3. Deaths and Hospitalizations

All deaths and hospitalizations will be recorded at Day 1 post dose and throughout the study as specified as part of AEs monitoring (see Section [6.5.7](#)) and per the Schedule of Assessments ([Table 1](#) and [Table 2](#)).

Reasons for deaths and hospitalizations will be adjudicated by an independent Adjudication Committee (see Section [3.8](#)).

6.2.4. Modified Body Mass Index (mBMI)

The nutritional status of patients is evaluated using the mBMI, calculated as the product of body mass index (BMI) (weight in kilograms divided by the square of height in meters) and serum albumin (g/L).

Weight, height, and serum albumin (collected as part of the serum chemistry panel) will be collected pre-dose at the timepoints specified in the Schedule of Assessments ([Table 1](#) and [Table 2](#)). The site will not perform the calculation for mBMI.

6.2.5. Cardiac Assessments

Manifestations of cardiac amyloid involvement will be assessed via cardiac biomarker, NYHA class, echocardiograms, CMR, and technetium scintigraphy imaging, as described.

Qualified personnel will be required to administer cardiac imaging assessments as specified in the respective reference manuals.

6.2.5.1. Cardiac Biomarkers

The cardiac biomarkers NT-proBNP and troponin I will be used to assess cardiac stress and heart failure severity. These biomarkers have been shown to be prognostic of outcomes in HF, including in ATTR amyloidosis.[[Damy 2016](#); [Kristen 2017](#); [Merlini 2016](#)] Blood samples will be drawn to measure cardiac biomarker levels at the timepoints specified in the Schedule of Assessments ([Table 1](#) and [Table 2](#)) and will be measured at a central laboratory. At screening Visit 1, only NT-proBNP will be assessed for eligibility purposes.

Details on cardiac biomarker sample collection, processing, and storage will be provided in a Study Laboratory Manual.

6.2.5.2. ATTR Amyloidosis Disease Stage

Based on published data from Gillmore et al, the ATTR amyloidosis disease staging used for this protocol stratifies patients with ATTR amyloidosis with cardiomyopathy (both hATTR and wtATTR) into prognostic categories using the serum biomarkers NT-proBNP and eGFR.[[Gillmore 2018](#)] Patients are categorized as follows:

- Stage 1 (lower risk): NT-proBNP \leq 3000 ng/L and eGFR \geq 45 ml/min/1.73 m²
- Stage 2 (intermediate risk): all other patients not meeting criteria for Stages 1 or 3
- Stage 3 (higher risk): NT-proBNP $>$ 3000 ng/L and eGFR $<$ 45 ml/min/1.73 m²

Based on published data, this staging system discriminates between patients with median survival of ~6 years, ~4 years, and ~2 years for Stage 1, Stage 2, and Stage 3, respectively.

6.2.5.3. New York Heart Association (NYHA) Class

NYHA class is a clinical assessment of symptoms resulting from HF and is assessed according to the table in Section [10.2](#). NYHA class will be evaluated at the timepoints specified in the Schedule of Assessments ([Table 1](#) and [Table 2](#)). The score collected at screening will be used to determine eligibility.

6.2.5.4. Echocardiogram

Echocardiographic parameters will be used for assessment of cardiac structure and function. Echocardiograms will be performed at the timepoints specified in the Schedule of Assessments ([Table 1](#) and [Table 2](#)), and analyzed at a central cardiac imaging core lab.

Image acquisition, storage, and transfer guidelines will be provided in the relevant study manual.

6.2.5.5. Technetium Scintigraphy Imaging

At select sites, in a subset of approximately 100 patients, technetium scintigraphy will be collected according to the Schedule of Assessments ([Table 1](#) and [Table 2](#)), as an optional exploratory imaging assessment, to assess cardiac amyloid involvement. Based on local practice standards, either ^{99m}Tc-3,3-diphosphono-1,2-propanodicarboxylic acid [DPD-Tc], ^{99m}Tc-pyrophosphate [PYP-Tc], or ^{99m}Tc-hydroxymethylene diphosphonate (^{99m}Tc-HMDP) can be used as the tracer. Technetium scintigraphy images will be interpreted at a central imaging core laboratory. Image acquisition, storage, and transfer guidelines will be provided in the relevant study manual.

For patients in whom technetium scintigraphy is performed as a study efficacy parameter, the results of the baseline scan must be reviewed by the central reader and confirmed to be consistent with the diagnosis of ATTR amyloidosis prior to randomization.

At select sites where technetium scintigraphy is being performed as an exploratory efficacy assessment, patients may be exempt from the baseline scan if technetium scintigraphy has been performed prior to study entry as part of the patient's clinical care within 6 months prior to the baseline assessment. In such cases, the historical technetium scintigraphy examination performed prior to study entry as part of the patient's clinical care should be collected and transferred to the central imaging core laboratory for interpretation; if the historical scan cannot be transferred to the central reader, or is deemed by the central reader to be of inadequate quality for interpretation, the patient should not participate in this optional efficacy assessment.

6.2.5.6. Cardiac Magnetic Resonance (CMR)

At select sites, in a subset of patients (≤ 60 patients), CMR will be collected according to the Schedule of Assessments ([Table 1](#) and [Table 2](#)), as an optional exploratory imaging assessment to assess cardiac amyloid involvement. CMR imaging with late gadolinium enhancement will only be performed on patients without contraindications (ie, pacemakers, severe renal failure with eGFR <30 mL/min/1.73 m², defibrillators, or allergy to gadolinium).

Details for image acquisition and upload for central review can be found in the relevant study manual.

6.2.6. Norfolk Quality of Life – Diabetic Neuropathy (Norfolk QoL-DN)

The Norfolk QoL-DN questionnaire is a standardized 35-item patient-reported outcomes measure that assesses 5 domains: physical function, large-fiber neuropathy, activities of daily living, symptoms, small-fiber neuropathy, and autonomic neuropathy. The total score ranges from -4 (best possible quality of life) to 136 points (worst possible quality of life). [[Vinik 2005](#); [Vinik 2014](#)]

The Norfolk QoL-DN questionnaire will be completed at the timepoints specified in the Schedule of Assessments ([Table 1](#) and [Table 2](#)).

6.2.7. Polyneuropathy Disability (PND)

Physician assessment of ambulation via PND score [Coutinho 1980; Yamamoto 2007] will be evaluated only at screening to assess eligibility for the study as specified in the Schedule of Assessments ([Table 1](#)). PND scoring is described in Section [10.1](#).

6.3. Pharmacodynamic Assessments

In this study, serum samples for measurement of TTR levels will be collected for the assessment of PD effects. TTR levels will be determined by a validated enzyme-linked immunoassay (ELISA). Details regarding sample volumes to be collected, and the processing, shipping, and analysis of the samples will be provided in the Laboratory Manual.

For this assessment, blood samples will be collected prior to dosing according to the timepoints specified in the Schedule of Assessments ([Table 1](#) and [Table 2](#)).

6.4. Pharmacokinetic Assessments

Blood samples will be collected for assessment of plasma concentrations of ALN-18328 (siRNA component of patisiran) and 2 lipid excipients (DLin-MC3-DMA and PEG₂₀₀₀-C-DMG) during the double-blind period at the timepoints specified in the Schedule of Assessments ([Table 1](#)). Plasma PK samples will be collected: predose (within 1 hour of planned study drug dosing); at the end of the infusion (+5 minutes); and 30 minutes after the end of the infusion (+15 minutes) at the specified visits.

For patients who discontinue treatment early during the double-blind period, a single PK sample will be taken at any time during the Early Treatment Discontinuation Visit, per the Schedule of Assessment ([Table 2](#)).

Actual dates and times of sample collection will be recorded.

Plasma concentrations of the 3 analytes will be determined using validated assay methods. Details regarding sample volumes to be collected, and the processing, shipping, and analysis of the samples will be provided in the Laboratory Manual.

PK parameters will be analyzed, whenever possible, as outlined in Section [7.2.7](#).

6.5. Safety Assessments

The assessment of safety during the study will consist of the surveillance and recording of AEs, including SAEs, recording of concomitant medication and measurements of vital signs, weight and height, ECG findings, and laboratory tests. Clinically significant abnormalities observed during the physical examination are recorded.

Safety will be monitored over the course of the study by the Sponsor's Medical Monitors and Medical Monitors at the designated contract research organization in addition an independent DMC as described in Section [3.7](#).

6.5.1. Vital Signs

Vital signs will be measured as specified in the Schedule of Assessments ([Table 1](#) and [Table 2](#)) and include blood pressure, heart rate, body temperature, and respiratory rate. Vital signs will be

measured predose, when applicable. When vital signs and blood sample collection occur at the same time, vital signs should be performed before blood samples are drawn, where possible. Vital signs should be measured predose in the seated or supine position, after the patient has rested comfortably for 10 minutes. Blood pressure should be taken using the same arm. Body temperature in degrees Celsius will be obtained via oral, tympanic, or axillary methods. Heart rate will be counted for a full minute and recorded in beats per minute, and respiration rate will be counted for a full minute and recorded in breaths per minute.

Additional vital sign assessments, as medically indicated, may be added at the discretion of the Investigator, or as per DMC advice (as applicable).

Vital signs results will be recorded in the eCRF.

6.5.2. Weight and Height

Height will be measured in centimeters. Body weight will be measured in kilograms. Height and body weight measurements will be collected as specified in the Schedule of Assessments ([Table 1](#) and [Table 2](#)) and will be recorded in the eCRF.

6.5.3. Physical Examination

Full and symptom-directed physical examinations will be conducted according to the Schedule of Assessments ([Table 1](#) and [Table 2](#)); if a physical examination is scheduled for a dosing visit, it should be conducted prior to dosing. Full physical examinations will include the examination of the following: general appearance; head, eyes, ears, nose and throat; respiratory, cardiovascular, gastrointestinal, musculoskeletal, and dermatological systems; thyroid; lymph nodes; and neurological status.

Symptom-directed physical examinations will be guided by evaluation of changes in symptoms, or the onset of new symptoms, since the last visit.

Clinically significant abnormalities observed during the physical examination are recorded on the medical history or AE eCRF.

6.5.4. Electrocardiogram

12-lead ECGs reporting rhythm, ventricular rate, RR interval, PR interval, QRS duration, and QT interval will be obtained, as specified in the Schedule of Assessments ([Table 1](#) and [Table 2](#)). Patients should be supine for at least 5 minutes before each ECG is obtained. The 12-lead ECGs will be performed in triplicate at baseline, with readings approximately 1 minute apart. At all other time points, a single 12-lead ECG will be performed.

When ECG and blood sample collection occur at the same time, ECGs should be performed before blood samples are drawn, when possible.

The Investigator or qualified designee will review all ECGs to assess whether the results have changed since the Baseline visit and to determine the clinical significance of the results. These assessments will be recorded in the eCRF. Additional ECGs may be collected at the discretion of the Investigator. Recordings will be archived in the patient's files.

6.5.5. Clinical Laboratory Assessments

The following clinical laboratory tests will be evaluated by a central laboratory. For any other unexplained clinically relevant abnormal laboratory test occurring after study drug administration, the test should be repeated and followed up at the discretion of the Investigator, until it has returned to the normal range or stabilized, and/or a diagnosis is made to adequately explain the abnormality. Additional safety laboratory tests and assessments as indicated by the clinical situation may be requested. Clinical laboratory assessments are listed in [Table 3](#) and will be assessed as specified in the Schedule of Assessments ([Table 1](#) and [Table 2](#)).

While local laboratory results may be used for urgent clinical and dosing decisions, on the day of the clinic visit assessments, all laboratory assessments specified in [Table 3](#), which are performed at the clinic should also be sent in parallel to the central laboratory. In the case of discrepant local and central laboratory results on samples drawn on the same day, central laboratory results will be relied upon for clinical and dosing decisions.

For any safety event or laboratory abnormality, additional laboratory assessments, imaging, and consultation may be performed for clinical evaluation and/or in consultation with the Medical Monitor; results may be collected and should be included in the clinical database.

Table 3: Clinical Laboratory Assessments

Hematology	
Complete blood count with differential	
Serum Chemistry	
Sodium	Potassium
BUN	Phosphate
Uric acid	Albumin
Total protein	Calcium
Glucose	Carbon dioxide
Creatinine and eGFR (using the MDRD formula)	Chloride
Liver Function Tests	
AST	ALP
ALT	Bilirubin (total and direct)
Coagulation (at Screening)	
Prothrombin time	International Normalized Ratio
Partial Thromboplastin Time	
Immunogenicity (see Section 6.5.5.1)	
Antidrug antibodies	
Pregnancy Testing/FSH Screening (see Section 6.5.5.2)	
β-human chorionic gonadotropin (females of child-bearing potential only)	Follicle-stimulating hormone (postmenopausal women only)

Abbreviations: ALP=alkaline phosphatase; ALT=alanine aminotransferase; AST=aspartate aminotransferase; BUN=blood urea nitrogen; eGFR=estimated glomerular filtration rate; FSH=follicle-stimulating hormone; MDRD=modification of diet in renal disease; PCR=polymerase chain reaction; RBCs=red blood cells; RNA=ribonucleic acid.

6.5.5.1. Immunogenicity

Serum samples will be collected to evaluate the presence of antidirug antibodies (ADA) as outlined in the Schedule of Assessments ([Table 1](#)). Details regarding the blood volume, processing, shipping, and analysis of the samples will be provided in the Laboratory Manual.

A validated ELISA will be used that specifically detects antibodies to PEG₂₀₀₀-C-DMG, which is a component of patisiran-LNP. Serum samples will first be analyzed with a screening assay. Samples testing positive for ADA in the screening assay will be further evaluated in a confirmatory assay. For the samples that tested positive for ADA in the confirmatory assay, the ADA titer will then be determined as the reciprocal of the highest dilution of the sample that yielded a positive ADA test result.

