3. INVESTIGATIONAL PLAN

3.1. Summary of Study Design

This is a Phase 3, randomized (1:1), double-blind, placebo-controlled, multicenter study to evaluate the efficacy and safety of patisiran in approximately 300 patients with ATTR amyloidosis (hereditary or wt) with cardiomyopathy. Approximately 20% of the study population is anticipated to have hATTR and 80% wtATTR. In addition, at baseline, patients are either:

- Tafamidis naïve; or
- Currently on tafamidis (for ≥ 6 months), with disease progression in the opinion of the investigator. This group will be capped at 30% of total enrollment in the study.

In addition to patients who have never taken tafamidis, patients who have been on tafamidis for ≤ 30 days total and have not received any tafamidis in the 6 months prior to baseline will be considered tafamidis naïve for this study.

The study consists of a screening period of up to 45 days, a 12-month, double-blind, placebo-controlled period, a 12-month, open-label extension period (during which all patients will receive patisiran), and a 28-day follow-up period (Figure 1).

After screening, during the 12-month double-blind period, eligible patients will be randomized to receive IV treatment every 3 weeks with either patisiran (0.3 mg/kg for patients weighing <100 kg; 30-mg fixed dose for patients weighing ≥ 100 kg) or placebo. Prior to receiving

randomized, double-blind study drug (patisiran or placebo), to reduce the potential for an IRR with patisiran, all patients will receive premedications at least 60 minutes before the start of their infusion. (Patients randomized to placebo will also receive premedications to maintain the blind.) Study drug will be administered in the clinic as an approximately 80-minute IV infusion.

During the 12-month open-label extension period, all patients will receive treatment with open-label patisiran. Furthermore, patients who have received ≥ 3 consecutive doses of patisiran on this study at the clinical site with no evidence of IRRs or other drug-related adverse effects impacting safety and tolerability of the infusion may have patisiran administered at home, where applicable country and local regulations allow. Home administration of patisiran will be performed by a healthcare professional trained on the protocol and on administration of premedications and patisiran infusion.

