3.5. Method of Assigning Patients to Treatment Groups

Using the interactive response system (IRS), patients will be randomized 1:1 to the patisiran or placebo arm. Randomization will be stratified by:

1. Baseline tafamidis (yes vs no)
2. Genotype (hATTR vs wtATTR amyloidosis with cardiomyopathy)
3. NYHA Class I or II **and** age < 75 years vs all other

Each patient will be uniquely identified in the study by a combination of the site number and patient identification number. Upon signing the informed consent form (ICF), the patient will be assigned a patient identification number by the IRS. The Investigator or his/her designee will contact the IRS to randomize the patient after confirming that the patient fulfills all the inclusion criteria and none of the exclusion criteria.

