4.3.4. Replacement of Study Patients

Patients who discontinue the study drug or stop participation in the study will not be replaced.

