7.1. Determination of Sample Size

The planned enrollment for this study is 300 patients. For the change from baseline at Month 12 in the 6-MWT, assuming a treatment difference of 33 meters between patisiran and placebo in the treatment-naïve group and 20 meters in patients with baseline tafamidis, the weighted average treatment difference between patisiran and placebo in the overall population is approximately 29 meters (standard deviation = 75 meters) assuming 70% are in the treatment-naïve group and 30% are in the baseline tafamidis group. A sample size of 300 patients provides >90% power for a 2-sided test to detect a mean difference between treatment groups at a 2-sided alpha = 0.05. Additional patients may be enrolled based on a recommendation to increase the sample size in the interim assessment ([Section 7.2.10](#)).

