7.2.9. Immunogenicity Analyses

The frequency and percentage of patients with confirmed positive ADA assay at any time during study as well as at each scheduled visit will be summarized. The titer results for patients with

confirmed positive ADA results will be summarized. The impact of ADA on PK, PD, efficacy and safety endpoints will be explored. Details will be described in the SAP.

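### ADA sampling is tied to the double-blind schedule only, so placebo patients who move to patisiran have no scheduled ADA sample after first exposure

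*Protocol*

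**What the plan says.** Section 6.5.5.1 of the protocol, in the Amendment 1 text, reads "Serum samples will be collected to evaluate the presence of antidirug antibodies (ADA) as outlined in the Schedule of Assessments" and names Table 1 only. Neighbouring sections on TTR (6.3), ECG (6.5.4), pregnancy testing (6.5.5.2) and vital status (6.5.6) each cite Tables 1 and 2.

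The ADA row of Table 1 is legible in the April 2019 protocol: samples are taken before dosing, for all randomized patients, from baseline onward. Table 2 in Amendment 1 goes from hematology directly to the pregnancy test, with no ADA row between them. Its Early Treatment Discontinuation column carries TTR and plasma PK, and Section 6.4 confirms the PK sample in prose for patients who stop during the double-blind period.

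Section 3.1 says: "During the 12-month open-label extension period, all patients will receive treatment with open-label patisiran". Section 5.2.3.2 puts the first open-label dose at Week 54. Section 2 lists the frequency and titer of ADA as an endpoint and gives no time limit. Section 7.2.9 plans to summarise "The frequency and percentage of patients with confirmed positive ADA assay at any time during study" and to explore how ADA relates to PK, PD, efficacy and safety.

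**The concern.** The ADA assay detects antibodies to PEG2000-C-DMG, a lipid component of patisiran. Placebo patients do not meet that component until Week 54, after the last scheduled ADA sample. Their Table 1 samples can show pre-existing antibody but cannot show antibody induced by the drug.

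For treatment-emergent ADA, the study therefore learns only from the patients randomized to patisiran, and only from their first year. Up to half of all patients ever exposed contribute nothing to that part of the endpoint, nor to any comparison of later infusion reactions or PD response by ADA status. Patients who stop early have a PK sample at the discontinuation visit with no ADA sample scheduled beside it.

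The statistical analysis plan can define open-label analyses, but it cannot recover blood that was never drawn. The gap therefore belongs to the protocol.

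**Working it through.** **Inputs from the protocol**
- Section 7.1: "The planned enrollment for this study is 300 patients".
- Section 3.5: "patients will be randomized 1:1 to the patisiran or placebo arm".
- Section 7.1: a difference of "approximately 29 meters (standard deviation = 75 meters") and a sample size that "provides >90% power for a 2-sided test to detect a mean difference between treatment groups at a 2-sided alpha = 0.05".
- Section 4.3.4: "Patients who discontinue the study drug or stop participation in the study will not be replaced". No dropout rate is given, so a loss of 0 to 20% before Week 54 is assumed.
- Table 2: open-label doses every 3 weeks from Week 54 (Day 379) to Week 105 (Day 736).

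**The plan's own figure.** With 150 per arm, the standard error is 75 × √(2/150) = 8.66 m. Power is Φ(29/8.66 − 1.96) = Φ(1.39) ≈ 91.8%, which agrees with the stated figure of more than 90%. This supports 150 per arm as the planned size. The protocol states no ADA sample count to reproduce.

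**Patients with no scheduled post-exposure ADA sample**
- No loss: 300 × 1/2 = 150; share of all ever exposed = 150/(150 + 150) = 50%.
- 20% loss: 150 × 0.8 = 120; share = 120/(150 + 120) = 44%.

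**Unsampled exposure per former placebo patient.** (736 − 379)/21 + 1 = 18 scheduled open-label doses.

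**Precision.** With no positives among n patients, the one-sided 95% upper bound is 1 − 0.05^(1/n):

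| Patients with a post-exposure ADA result | n | Upper bound |
|---|---|---|
| As scheduled (patisiran arm only) | 150 | 2.0% |
| Open-label sampling added, 20% placebo loss | 270 | 1.1% |
| Open-label sampling added, no loss | 300 | 1.0% |

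These bounds take every patient randomized to patisiran as having at least one ADA result after dosing.

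**Cross-references side by side.** Section 6.5.5 says the tests in Table 3, which include antidrug antibodies, follow Tables 1 and 2. Section 6.5.5.1 says Table 1. The Table 2 footnote expands the abbreviation ADA, but no row in the legible grid uses it. The document gives no reason for ending ADA sampling with the double-blind period.

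**The case against.** **The text may not be the one in force.** Sections 6.5.5.1 and Table 2 are quoted from Amendment 1. Amendment 2 revised Section 6.5, and its full protocol is not in the text reviewed. The table grids are also damaged in extraction. This caution stands. However, the prose of 6.5.5.1 is intact and points to Table 1 independently of the grid. The Amendment 2 summary of changes allows offsite ADA collection but lists no new open-label ADA time points.

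**Limiting ADA to the controlled period is coherent.** Scheduled PK sampling is confined in much the same way (Section 6.4), and stored exploratory or residual samples (Section 6.6) might allow later testing. This stands in part. Storage depends on consent and local rules, and no ADA assay of stored samples is planned.

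The documents do not support several stronger readings that a reader might infer:

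- *Placebo patients go wholly untested for ADA.* They do not: Table 1 gives them samples at baseline and through the double-blind period. Only post-exposure samples are missing.
- *Reactions at a former placebo patient's first patisiran dose cannot be related to ADA.* Antibody relevant to a first dose must already be present, and the Table 1 samples inform that. What is missed is antibody induced later.
- *Section 7.2.9 contradicts the schedule.* The phrase "The frequency and percentage of patients with confirmed positive ADA assay at any time during study" looks unlimited, but Section 7.2 introduces its contents as summaries for the analysis at the end of the 12-month double-blind period and leaves open-label analyses to the SAP. The conflict is weak.
- *The reported ADA percentage would be diluted by unsampled patients.* Section 7.2.9 states no denominator and no pooling of arms, and leaves details to the SAP.
- *Early stoppers lose all ADA follow-up.* Section 4.3.1 encourages them to complete assessments through Month 12, excluding only PK. What is missing is an ADA sample paired with the discontinuation PK sample.

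**Conclusion.** The sampling gap holds for the legible text. At most 150 former placebo patients (120 to 150 if 0 to 20% are lost before Week 54), who are 44 to 50% of those ever exposed, would receive up to 18 patisiran doses with no scheduled ADA sample. The cost is limited precision on treatment-emergent ADA: a zero-event upper bound of 2.0%, against 1.0 to 1.1% if they were sampled. No primary or ranked secondary efficacy comparison is affected.

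This is a cheap improvement worth making, not a flaw that undermines the trial. It rests on Table 2 in force having no ADA row, on the planned 300 patients at 1:1, and on an attrition range that the protocol does not supply.

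**What to change.** First check the Schedule of Assessments in Amendment 2. If it still has no open-label ADA sampling:

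1. Add an ADA row to Table 2 at the open-label visits where TTR blood is already drawn, and at the Early Treatment Discontinuation Visit, where TTR and PK are already taken.
2. Make Section 6.5.5.1 cite Tables 1 and 2, which also brings it into line with Section 6.5.5.

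The cost is one extra serum aliquot at existing draws and the ADA assays for up to about 300 patients. No dosing or clinical rule changes, and Section 7.2.9 needs no rewording for this purpose.
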